Any patients with evidence of study drug related adverse events at follow-up will be reviewed by the Data and Safety Monitoring Committee (DSMC) to review all the supporting evidence. The (DSMC) will consist of at least one anesthesiologist, one surgeon and a statistician not otherwise associated with the trial. Their role will be to review the available evidence provided by the research coordinator for the follow-up of all patients including in-hospital and follow-up study drug related adverse events. The outcomes of interest are listed above and will follow-strict study definitions as outlined. All outcomes will be based on consensus of the DSMC.

There will be an interim analysis performed by the Data and Safety Monitoring Committee. This analysis will be conducted when half of the patients have been enrolled. The final analysis will be conducted once all enrolled patients have reached their follow-up date. All final analysis will take into consideration that an interim analysis was conducted.

In case the study is terminated prematurely, the REB will be notified within 14 days in writing including the reason for the termination. If the termination is related to an emergent safety issue, the notification will be faxed to the REB office or preceded by a telephone call to the Chair or REB Coordinator. The study will be unblinded and all patients having received fibrinogen concentrate will be notified in writing and by direct contact via a telephone call of the study termination as well as

Capital Health

the reason for termination. Patients will also be informed of any emergent safety issues or adverse outcomes. Patients will be instructed on how to proceed in terms of medical care and follow up investigations.

RANDOMIZATION METHOD

Informed consent will be obtained from the patient prior to the operation either in the same-day surgery clinic or at the bedside if the patient has already been admitted to hospital pre-operatively. The randomization process will be performed with the help of software (G*Power version 3.1.2). Treatment allocation cards will be provided by the study Sponsor and placed in sealed, opaque envelopes for safe storage in a secure location to preserve the integrity of the blinding. The study drug designate will withdraw the envelope directing the patient's randomization to the FIB group or the PLACEBO group. Both the surgeon and anaesthesiologist will be blinded to patient randomization.

Randomization process

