After eligibility and written informed consent is confirmed patients will be randomized on the day of surgery after arrival at the OR to receive either fibrinogen concentrate or placebo after heparin reversal as indicated in the algorithm (Figure 3). If the patient has a diffuse medical bleed then the research coordinator will be called to inform The research coordinator study drug designate will call the study drug designate to randomize the patient and a sequential envelope will be opened by them in the blood bank. The drug/placebo will be prepared in the Blood Transfusion Services at the Infirmary site. The drug/placebo will be transported to the OR by the study drug designate.

Dosage and Dosage Regimen

The dose of fibrinogen concentrate will be calculated based on the point of care measurement of maximum clot firmness (MCF)

Capital Health

in the FIBTEM® test performed on CPB (aortic cross clamp off)¹⁰. According to the available literature we will use the following formula to achieve the preoperative (baseline) FIBTEM MCF (mm):

$$\text{Fibrinogen dosage (g)} = [\text{Preop FIBTEM MCF (mm)} - \text{FIBTEM MCF (mm)}] \times \text{bodyweight (kg)} \times c$$

$$C = \frac{0.5 \text{ g}}{1(\text{mm}) \times 70}$$

70

The formula can be simplified to:

$$(\text{Preop FIBTEM MCF} - \text{FIBTEM MCF}) \times \text{bodyweight}/140.$$

Calculation example: A patient's bodyweight is 75kg. The baseline FIBTEM MCF showed 22mm. The FIBTEM test on CPB shows a MCF of 10 mm. The overall dose of concentrated fibrinogen to achieve the baseline MCF of 22 mm would be:

$$\text{Fibrinogen dosage (g)} = (22 - 10) \times 75/140 = 12 \times 75/140 = \mathbf{6.4}$$

Fibrinogen dosing will be based on the results of the FIBTEM® analysis. The amount of fibrinogen concentrate corresponds to approximately 0.5 g of fibrinogen concentrate needed to raise MCF by 1 mm in a 70 kg patient^{9,10,26}. The maximum fibrinogen concentrate dose used in this study will be 10 g. If the baseline FIBTEM® is ≤ 12 mm the fibrinogen dosage will be calculated **from a minimum baseline value of 15 mm to achieve a more effective fibrinogen dosage**. In the placebo group, the standard hemostatic algorithm involving the use of plasma, Cryo and platelets (Figure 3), will be used as per the standard of care currently in place at CDHA.

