As per the standard of care in this surgical population, all post-operative cardiac surgery patients will be taken immediately to a dedicated cardiovascular intensive care unit (CVICU). All patients will receive respiratory and hemodynamic support as needed. Each patient will be required to meet standard hospital criteria both prior to extubation and prior to transfer to the intermediate-care unit (IMCU). Discharged patients will be transferred to an intermediate-care unit or general-care ward under the care of the same cardiac surgical team. All patients will be monitored continuously for a minimum of 24 hours. In case of a post-operative bleeding in CVICU the same algorithm (Figure 3) like in the OR will be used. In case of surgical bleeding a re-sternotomy will be performed. Diffuse bleeding will be treated with blood components (step 2 -5, Figure 3). Patients having a valve replaced with a mechanical valve will receive heparin or warfarin 48 hours after surgery. All other patients will get ASA (acetylsalicylic acid, Aspirin®, Bayer Canada) on the first postoperative day (anticoagulation protocol, Division of Cardiac Surgery, QEII, Halifax, Canada).

ASSESSMENT OF SAFETY

Adverse Events

The following treatment-emergent and adverse effects will be captured during this study from the date ~~the consent was signed~~ of randomization to the 6 month follow-up:

Treatment-emergent adverse events

- Pleural effusion
- Atrial fibrillation
- Postoperative Delirium
- Reoperation because of surgical bleeding and unknown bleeding
- Air embolism

Adverse events (A/E) and Serious adverse events (SAE)

- Anaphylaxis
- Stroke
- Myocardial infarction
- Pulmonary embolism
- Deep vein thromboembolism
- Sternal wound infection
- Recurrent angina
- Angiography
- Percutaneous coronary intervention (PCT)
- Repeated cardiac surgery
- Cardiorespiratory arrest
- Cerebral hemorrhage
- Death

All serious unexpected adverse drug reactions will be reported to Health Canada as per ICH/GCP guidelines.

Unblinding

Unblinding for this study will occur when:

1. Clinical treatment decisions need to be made and when an unexpected serious adverse event occurs and the intervention must be made known.
2. At the request of the Data Safety Monitoring Committee.

Capital Health

3. After 110 participants have reached the primary endpoint for interim analysis.
4. At the conclusion of the study to determine the effect of the intervention.

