Approximately 200 complex cardiac procedures are performed annually in Halifax by nine cardiac surgeons. Of these patients, conflicting studies and patients being disqualified on the basis of exclusion criteria will result in a maximal annual number of eligible patients of 100 per year. We would plan to recruit 222 patients for this study. With a length of follow up of 6 months and using administrative data of an already well established data base we are expecting a rate of loss under 5%.

DATA HANDLING AND RECORD KEEPING

Data will be collected from patient charts and health records, the anesthetic record as well as the Maritime heart center cardiac surgery database. A data collection sheet will be filled out by the study nurse for patients included in the study. Follow-up data will be collected from patients themselves. In cases where patients have adverse outcomes, this information will be obtained from hospital records and the patient.

A data collection form will be used to collect study information and will be completed by the designated study personnel for participants. These forms will be detailing demographic characteristics, intra-operative, postoperative and follow-up outcomes. Individual data forms will record: the perioperative amount of blood products used (packed red cells, FFP, platelets,

Capital Health

Cryo). Also fibrinogen levels, hematocrit, PTT, INR, platelet count, Hemoglobin, Thromboelastometry (ROTEM®, CT, CFT, Angle, MCF), CVICU-stay, Hospital-stay, In-Hospital Mortality, Hemoglobin, adverse events (anaphylaxis, stroke, myocardial infarction, pulmonary embolism, and deep vein thromboembolism) and usage of factor VII concentrate and human prothrombin complex will be collected for study purposes. All data will be reviewed by the appropriate **outcome** committee. Once reviewed all data will be entered and maintained electronically on a designated CDHA computer.

Data will also be collected using the Maritime Heart Center (MHC) cardiac surgery database. This database is a prospectively collected, clinical database that captures detailed information on a wide range of pre-operative, intra-operative, and in-hospital postoperative variables including post-operative complications and in-hospital mortality for all patients undergoing cardiac surgery at the QE II Health Sciences Center.

QUALITY CONTROL AND QUALITY ASSURANCE PROCEDURES

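### Safety capture is a fixed list of 18 events with no category for other serious events, so a serious unlisted event not judged drug-related may be missing from the trial data and the arm comparison

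*Combined protocol and SAP*

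**What the plan says.** The Adverse Events section sets the capture rule: "The following treatment-emergent and adverse effects will be captured during this study", over a window that runs from the date "of randomization to the 6 month follow-up". It then names five items under a treatment-emergent heading and 13 under adverse and serious adverse events. Neither list ends with an open category, and the term treatment-emergent is not defined.

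The next line adds a reporting duty: "All serious unexpected adverse drug reactions will be reported to Health Canada as per ICH/GCP guidelines". The Unblinding section allows the code to be broken "when an unexpected serious adverse event occurs and the intervention must be made known". Under Methodology, and again under After Discharge Follow-up, patients with evidence of drug-related adverse events are referred to the Data and Safety Monitoring Committee (DSMC). On the outcomes that it considers, the Methodology section says "The outcomes of interest are listed above and will follow-strict study definitions as outlined".

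Data Handling and Record Keeping names five adverse events for the data form: anaphylaxis, stroke, myocardial infarction, pulmonary embolism and deep vein thromboembolism. Table 2 shows the same five at discharge and a fixed list of nine items at each of the 6-week, 3-month and 6-month contacts.

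On timing, the Randomization process section says "patients will be randomized on the day of surgery after arrival at the OR". Treatment of Subjects places study drug after weaning from bypass, heparin reversal and surgical hemostasis.

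**The concern.** A list finds only what its authors foresaw. The plan commits itself to acting on unexpected serious events but describes no field or procedure by which such an event would first be recorded. What is at stake is the comparison of randomised arms. An unsuspected harm usually appears as an imbalance in events that no clinician attributed to the drug. If those events are recorded only when someone suspects the drug, the imbalance cannot be seen. This matters here because the Risks section itself says that no published study clearly addresses the risk of fibrinogen supplementation.

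A smaller matter is that the window opens on the date of randomisation, while study drug follows bypass and protamine. Events that the drug cannot have caused may therefore fall inside the window.

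**Working it through.** **1. The list.** Five treatment-emergent items (pleural effusion, atrial fibrillation, postoperative delirium, reoperation for bleeding, air embolism) plus 13 others gives 5 + 13 = 18. Acute kidney injury is not among them. Nor is acute lung injury or ARDS, and the only infection is sternal wound infection. Yet the sections on the need for a trial and on benefits argue for it through lung injury and nosocomial infection after transfusion.

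**2. Other routes for an unlisted serious event.**

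| Route | What it covers | What it needs first |
|---|---|---|
| Report to Health Canada | Serious unexpected drug reactions | Event noticed and judged drug-related |
| DSMC review | Drug-related adverse events | Evidence supplied by the research coordinator, and the same judgement |
| Unblinding | Unexpected serious events where the allocation must be known | Event noticed; this is not a data-capture step |
| Follow-up contacts (Table 2) | Nine fixed items; readmission only for heart failure, myocardial infarction or acute coronary syndrome | Event is on the list |
| Linked databases | Could hold more, but the 6-month extract names cardiac mortality, those same readmissions, and re-intervention | Event is in the extract |
| Cardiac surgery database, hospital records | In-hospital complications, adverse outcomes | No stated rule moving unlisted events into safety review or the arm comparison |

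A serious unlisted event judged drug-related has a route. One not judged drug-related has no stated route into the arm comparison.

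**3. Scale.** The plan recruits 222 patients, or 111 per group. Table 1's 111 reproduces: with a difference of 2.4 units, SD 5.9, two-sided 0.05 and 80% power, a t test needs 96 per group, and allowing for the minimum Mann-Whitney efficiency of 0.864 gives 111. The chance of at least one event in 111 fibrinogen patients at true rate p is 1 − (1 − p)^111. The rates of 0.5% to 3% are assumptions, because the documents give none for unlisted events:

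| p | Chance of at least one |
|---|---|
| 1 in 10,000 | 1.1% |
| 0.5% | 43% |
| 1% | 67% |
| 2% | 89% |
| 3% | 97% |

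The first row is the ceiling that the Risks section suggests for directly drug-related events. The other rows concern serious events of any cause.

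With open capture, 0 events in 111 patients gives a one-sided 95% upper bound of 1 − 0.05^(1/111) = 2.7%. With list-only capture, the absence of a record cannot be read as 0 of 111, so that bound is not available.

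**4. Timing.** If patients are randomised on arrival at the OR, induction, bypass and protamine all fall inside the window. Subject withdrawal criteria instead implies randomisation after the bleeding assessment, ten minutes after protamine. The gap is then short, although a rule based on the date still admits earlier events on the same day.

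The effect on power depends entirely on assumed rates. For post-drug events of 2% against 10% at 111 per arm, Fisher power is 65%. With an equal pre-drug background it is 64.5% (background 0.1%), 61% (0.5%), 51% (2%), 38% (5%) or 26% (10%). The documents give neither the event rates nor the background, so none of these figures is an estimate for this trial.

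**The case against.** A reader might infer that an unexpected serious reaction has nowhere to be recorded and would not reach the regulator. The documents do not support that. The duty to report such reactions follows directly after the list, DSMC referral is not tied to the 18 terms, and Data Handling says that adverse outcomes will be obtained from hospital records and the patient. The case report form is not among the documents, so the absence of an open field is inferred from the items named for it. The plan also never says that only the listed events will be recorded. All of this stands, and it narrows the point to serious events not judged drug-related.

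A reader might also infer that events before study drug are counted as treatment-emergent. The plan does not say so. Only five items carry that heading. Three are post-operative by name or nature, and air embolism is described as extremely rare and is also a reason for withdrawal, which leaves atrial fibrillation. Stroke, myocardial infarction, anaphylaxis and arrest sit under the other heading. The start point is the same in both arms, so it does not bias the comparison, and onset can be recovered from the anesthetic record, already a data source. What remains is a need for a definition.

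**Conclusion.** The point holds in a limited form. Followed as written, the plan captures 18 named events and has no category or stated procedure for other serious events, so a serious unlisted event not judged drug-related may be missing from the safety data and the arm comparison. This rests on reading the capture sentence together with the data-form items and Table 2, which agree in being fixed lists. The probabilities above show scale under assumed rates and do not predict any particular harm.

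Timing is secondary: an undefined term and a window that can include events before study drug, with no bias towards either arm and no effect on power that the documents allow to be quantified. Overall this is a cheap improvement of minor severity.

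**What to change.** 1. Reword the Adverse Events section to capture every serious adverse event, listed or not, from randomisation to the 6-month contact. Keep the 18 items as events of special interest.
2. Add one open field for any other serious event to the in-hospital form and to the 6-week, 3-month and 6-month contacts.
3. Record onset relative to the start of study drug, using the anesthetic record, and list events with earlier onset separately.
4. Reconcile the time of randomisation between Randomization process (on arrival at the OR) and Subject withdrawal criteria (after the bleeding assessment), since it fixes where the window opens.

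The cost is a wording change, one open field per form and an onset time, with no extra visits. The downside is more event forms after complex surgery, which a written list of expected post-operative events can limit.

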- intake of anti-clotting drugs within 2-5 days preoperatively (low dose ASA is allowed) based on the drug's half life or pharmacokinetic profile,
- allergy to concentrated fibrinogen or other components in the product,
- anemia (Hb < 110),
- diagnosed deep vein thrombosis (DVT),
- pulmonary embolism,
- acute stroke **(within the last 3 months)**,
- acute myocardial infarction (within the last 3 months),
- **any unstable medical condition as determined by the Principal Investigator**
- **within the past 30 days, participated in or currently enrolled in a clinical trial.**

Subject withdrawal criteria

Capital Health

As per the intraoperative algorithm (Figure 3) the Anesthesiologist and the Surgeon complete a bleeding assessment ten minutes after the protamine is given. If the patient is not having a diffuse medical bleed they will not be randomized and will be considered a screen failure. **Patients who are experiencing surgical bleeding after weaning from CPB and protamine administration with requirement of a second pump run are withdrawn from the study.** In case of an ongoing bleeding after step 3 of the study algorithm (Figure 3) an immediate and blinded FIBTEM is performed in order to prevent an overdosing of fibrinogen. If the FIBTEM shows an amplitude > 20 mm the patient will be unblinded and drop out of the study for safety reasons. This way it is ensured that a patient who received concentrated fibrinogen is not getting Cryoprecipitate (step 4 of study algorithm; Figure 3) leading to supraphysiologic levels of fibrinogen. Patients who have extremely rare complications like air embolism, heart perforation or heart lung machine failure will be ~~excluded~~ **withdrawn** from the study.

TREATMENT OF SUBJECTS

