The Blood Transfusion Services are able to unblind for the clinical treatment of a patient. Please refer to the site Standard operating procedure for more details of this process. If a patient's treatment is unblinded before the 24 hour primary end point their data will not be used in the analysis.

STATISTICS

Sample size

The primary outcome of interest will be overall need for blood transfusion at 24hr after surgery (including all used blood components from the start of surgery). For the sample size calculations G*Power version 3.1.2 was used.

Based on the available literature ^{9,10,12}, the investigator hypothesized a 70-90% reduction in total units of blood products in the group receiving fibrinogen compared with the group receiving conventional therapy. An estimate of blood product requirement in the group receiving conventional therapy is mean 3.4 units (standard deviation 5.9) based on our data from 2005 to 2007 for AVR+CABG, MVR+CABG, AVR+MVR, and Aortic root repair +/-AVR. Standard deviation 5.9 was used for both groups. Blood product requirement in the two groups will be compared using the Mann-Whitney U test for two independent samples. The sample size calculation was based on a two-tailed test with $\alpha = 0.05$, for $\beta = 0.2, 0.1, \text{ and } 0.05$. The sample sizes shown Table 1 represent the number of patients required in each group.

Details of the planned analysis

~~Individual case forms will be completed by the research coordinator for individual patients.~~ **The research coordinator will complete individual case forms for individual patients.** These forms will be detailing demographic characteristics,

Capital Health

intra-operative, post-operative and follow-up outcomes. Outcome data and blood samples will be collected according a lab/data schedule (Table 2). ~~All data will be reviewed by the appropriate clinical outcomes committee.~~ **The Sponsor will review all data.** Once reviewed all data will entered and maintained electronically.

Primary outcome: Blood component requirement in the two groups will be compared using the Mann-Whitney U test for two independent samples.

Secondary outcomes: Univariate comparisons between patients randomized to FIB and patients randomized to PLACEBO group will be carried out based on pre-, intra-, and post-operative variables using Chi-square tests for dichotomous variables, two-tailed t-tests for continuous variables and Wilcoxon rank sum tests for nominal variables.

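### Patients unblinded before 24 h are left out of the analysis, and the FIBTEM rule makes those losses depend on bleeding and probably on treatment arm

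*Combined protocol and SAP*

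**What the plan says.** Three sections act together.

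- **Assessment of Safety, Unblinding:** "If a patient's treatment is unblinded before the 24 hour primary end point their data will not be used in the analysis". The same section lists the grounds for unblinding, which include clinical treatment decisions, unexpected serious adverse events and a request from the monitoring committee.
- **Subject withdrawal criteria:** "In case of an ongoing bleeding after step 3 of the study algorithm (Figure 3) an immediate and blinded FIBTEM is performed". Then: "If the FIBTEM shows an amplitude > 20 mm the patient will be unblinded and drop out of the study for safety reasons". The stated aim is to prevent "a patient who received concentrated fibrinogen is not getting Cryoprecipitate (step 4 of study algorithm; Figure 3) leading to supraphysiologic levels of fibrinogen".
- **Post-operative management:** "In case of a post-operative bleeding in CVICU the same algorithm (Figure 3) like in the OR will be used". The check can therefore also arise in the CVICU, inside the 24 h endpoint window.

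Under Dosage and Dosage Regimen, fibrinogen is dosed to bring FIBTEM back to its preoperative value, while the comparator is saline. In the worked example the value on bypass is 10 mm: "The overall dose of concentrated fibrinogen to achieve the baseline MCF of 22 mm would be" 6.4 g.

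The Statistics section names a Mann-Whitney test for the primary outcome. It defines no analysis set of all randomised or all dosed patients and no sensitivity analysis, gives no expected number of unblindings, and does not ask for unblindings to be reported by arm.

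**The concern.** Removing patients after randomisation is harmless only if removal is unrelated to outcome or works the same way in both arms. Neither can be assumed here.

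- **Link to outcome.** Only patients who are still bleeding get the FIBTEM check, and bleeding drives the number of units transfused.
- **Link to arm.** The check is done blind and can be triggered in either arm, but it exists to identify patients who received fibrinogen, and only that arm receives a drug meant to raise FIBTEM. The patient in the worked example, if brought to 22 mm and still bleeding, is above 20 mm and is deleted. A saline patient bleeding just as much at 10 mm stays in, and every unit counts.

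The deleted patients would then be largely those whose fibrinogen was restored but who went on bleeding, which means treatment failures. The fibrinogen arm's unit count would fall without any drug effect. Because the plan does not call for unblindings by arm, a reader of the results could not tell a negligible case from a serious one.

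**Working it through.** **Inputs from the protocol.** Control mean 3.4 units, SD 5.9 in both arms, two-sided alpha 0.05, Mann-Whitney test (Sample size); 111 per group for 80% power at a 70% reduction (Table 1); 222 in total (Estimated Recruitment Rate).

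**The plan's own figure.** With d = 2.4/5.9 = 0.407 and the minimum asymptotic relative efficiency of 0.864 for the Mann-Whitney test, the effective size is 111 × 0.864 = 95.9 per arm. The noncentrality is 0.407 × √(95.9/2) = 2.82 and power is 0.800. The planned 111 per arm reproduces, and this point does not dispute it.

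**Assumptions (not in the documents).** Units follow a negative binomial distribution with the protocol's mean and SD. The documents give no loss fraction, so a range is shown.

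- k = 3.4² / (5.9² − 3.4) = 11.56/31.41 = 0.368, so P(0 units) = 0.425.
- P(≥6) = 0.201, P(≥8) = 0.146, P(≥10) = 0.109. These three cut-offs serve as alternative definitions of a heavy user.

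**Spurious reduction.** If a share f of heavy users is removed from the fibrinogen arm, its mean becomes (3.4 − f·P·M)/(1 − f·P), where M is the mean among heavy users. For the ≥6 cut-off M = 12.58. With f = 0.25 this is (3.4 − 0.631)/(1 − 0.050) = 2.92, a reduction of about 14% with no drug effect.

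**Type I error.** No drug effect, 111 per arm, tie-corrected Mann-Whitney, 20,000 simulated trials per setting (Monte Carlo standard error about 0.15 points at 5%). With nobody excluded the two-sided error is 4.9–5.1%. With loss in the fibrinogen arm only, ranges over the three cut-offs are:

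| Heavy users lost | Patients of 111 | Spurious reduction in mean | Two-sided error (nominal 5%) | One-sided error for fibrinogen (nominal 2.5%) |
|---|---|---|---|---|
| 5% | about 1 | 2–3% | 5.0–5.1% | 2.8–3.2% |
| 10% | 1–2 | 4–6% | 5.2–5.5% | 3.4–4.0% |
| 25% | 3–6 | 11–14% | 6.1–9.0% | 5.1–8.3% |
| 50% | 6–11 | 23–30% | 10–22% | 10–22% |

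**Dependence on the assumptions.**

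- If 10% of heavy placebo users are also lost, the 25% and 50% rows fall to 5.6–6.2% and 8.4–15.8% two-sided.
- If 25% are lost in each arm, error is 5.1%. If fibrinogen-arm loss is unrelated to bleeding, error is also 5.1%.
- Heavy use is not essential. Losing 2, 5 or 10 fibrinogen patients at random among those with at least 1 unit gives 5.1%, 6.0% and 8.8%, with spurious reductions of 1%, 4% and 7%. Among those with at least 3 units it gives 5.3%, 6.8% and 13.9%, with 3%, 8% and 16%.
- A second loss model, removing 2%, 5% or 10% of the fibrinogen arm from its heaviest fifth of users, gives 5.3%, 9.5% and 23.5% error, with 5%, 15% and 30% reductions.

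**The case against.** **Other routes could pull the other way.** Unblinding for a clinical treatment decision is not tied to an arm, and a placebo patient who keeps bleeding is a natural candidate. In the same model (≥6 cut-off), losing 10% of heavy fibrinogen users and 25% of heavy placebo users gives about 5.8% two-sided error, of which 4.8% is against fibrinogen. With 5% and 25% it is about 7.4%, of which 6.6% is against. This stands as a possibility, so the direction of the whole exclusion is less certain than that of the FIBTEM route. No text in the protocol supports that pattern, however, whereas the FIBTEM rule states its own target. A bias against fibrinogen would also be a reason to drop the exclusion.

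**The FIBTEM route may be rare.** It needs ongoing bleeding after step 3 and a value above 20 mm, both before 24 h. Dosing aims only at the patient's own baseline (or 15 mm when the baseline is at or below 12 mm), is capped at 10 g, and entry requires fibrinogen of at most 3.8 g/l. A dose that exactly meets its target therefore exceeds 20 mm only if the baseline did. This stands: the 22 mm example shows that it can happen, not how often.

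**The larger losses are assumed.** Figure 3 was not available to me, so nothing ties step 3 to a unit count. If the hypothesised 70% effect were real (mean 1.0, same shape), only about 1–4 of 111 fibrinogen patients would reach the cut-offs, against 12–22 with no effect. Withholding Cryo may also lower the totals of dropped patients. These points limit the size under a strong effect. They do not protect the error rate when the drug has little or no effect, which is what the test must guard against.

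The under-5% loss in the recruitment section is explained by length of follow-up and database use. It is not an unblinding rate.

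**Conclusion.** The concern holds. As written, the plan discards primary-endpoint data on randomised, dosed patients for a reason linked to bleeding and probably to arm. That this exclusion exists is certain from the text. That the FIBTEM route favours fibrinogen is an inference from its stated purpose and from the dosing rule. The size is unknown and may be negligible: with 1–2 patients lost, error stays near nominal. With about 5 or more lost from the fibrinogen arm it rises, and nearly all of the excess favours fibrinogen. These figures rest on a negative binomial distribution with the protocol's mean and SD, on assumed loss fractions, and on loss falling mainly in one arm.

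It must be fixed before analysis. The rule concerns the primary result, nothing in the plan would reveal which case applied, and correcting it needs no new data.

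**What to change.** Delete the sentence in the Unblinding section and put in its place:

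> The primary analysis includes every randomised patient who received study drug or placebo, in the assigned arm. All blood components given from the start of surgery until 24 h after study treatment are counted, whether or not the patient was unblinded or dropped under the FIBTEM rule.

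In addition:

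- Report the number unblinded before 24 h by arm and by reason.
- Keep the set without unblinded patients as a sensitivity analysis only.
- State under Subject withdrawal criteria that dropping out means leaving blinded study procedures, with the 24 h unit counts and the six-month safety follow-up retained.
- Note that the new wording also keeps dosed patients who are withdrawn under the other withdrawal rules. It can be used whether randomisation takes place on arrival in the operating room or after the bleeding assessment. Patients randomised but never dosed fall outside it and should be counted by arm.

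The cost is wording only, since Table 2 already schedules the unit counts at 24 h. There are two downsides. The observed effect may look slightly smaller, and units given once staff know the arm are included; the sensitivity analysis shows how much that matters. The clinical 20 mm rule is not changed, and I take no position on it.
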